6.1 Subject Screening and Enrollment

Potential study participants will be asked to sign an Informed Consent Form (ICF) prior to any study assessments. Screening should be completed within 28 days of Study Day 0; non-qualifying screening assessments (e.g.; specular microscopy) and screening assessments outside this window may be repeated. Screening assessments will include:

- Assessment of study eligibility,
- Medical and ocular history,
- BCVA assessment,
- Comprehensive ocular examination (slit lamp biomicroscopy and dilated examination of lens, fundus, and vitreous),
- Specular microscopy (including images of the central cornea),

If the subject is deemed preliminarily eligible by the Investigator, specular microscopy images of the central cornea will be sent to central image reading facility. If the reading center confirms that ECD is at least one eye is < 2000 cells/mm², a space is available in a cohort, and the subject meets all of the additional eligibility criteria, the subject will be randomized and additional baseline assessments obtained.

If both eyes qualify, the eye with the lowest visible cell count (per the central reading facility) will be designated as the Study Eye (SE). If both eyes have the same visible cell count, the right eye will be designated the SE.

All potential study subjects will be provided with a unique Subject ID Number (Subject ID) at the time of providing written informed consent. The Subject ID will consist of a unique 6-digit number (3-digit site number and a 3-digit subject number, separated by a hyphen [-]).

Figure 3: Subject ID Numbering

	Subject ID Number						
_	Site NumberSubject Number						
	9	9	9	-	9	9	9

For example, Subject ID 101-001 = The first participant consented at Site 101; 103-003 = The third participant consented at Site 103

Trefoil Therapeutics, Inc.	Clinical Study Protocol TTHX-001
Confidential and Proprietary	Amendment 1.0: September 8, 2020

Once a Subject ID number has been issued, it cannot be reused.

Subjects enrolled in and participating in the Observational Sub-study who are eligible may "roll-over" into the main study provided they meet all of the additional eligibility criteria, there is an open cohort, and they consent. Subjects who "roll-over" into the main study do not need to complete the remaining visits in the Observational Sub-study, and Observational Sub-study assessments may be used as screening assessments for the main study as long as they were performed within the protocol-specified timeframe.

Potential subjects may be rescreened or have repeat eligibility assessments, if appropriate.

6.2 Study Treatment Administration/ Intracameral Injection

This procedure can be performed by a qualified and trained investigator at the slit lamp microscope or in a procedure room setting. Subsequent injections should be performed in the same setting.

Materials:

Procedure:

After appropriate sterile prepping and draping,

Trefoil Therapeutics, Inc.	Clinical Study Protocol TTHX-001
Confidential and Proprietary	Amendment 1.0: September 8, 2020

6.3 Concomitant Medications and Treatments

6.3.1 Concomitant Medications

Subjects are expected to receive concomitant medications for the management of concurrent medical conditions. Medications taken during the 28 days prior until 28 days following the last study treatment administration will be recorded. Artificial tears are allowed during the study but other ocular medications must be discussed with the masked Medical Monitor.

6.3.2 **Prohibited Medications**

The following medications are prohibited:

Trefoil Therapeutics, Inc.	Clinical Study Protocol TTHX-001
Confidential and Proprietary	Amendment 1.0: September 8, 2020

- Rho-kinase inhibitors (topical or systemic, e.g.; Fasudil, Netarsudil [Rhopressa])
- Systemic or dermatological cytotoxic chemotherapy
- Hypertonic sodium chloride ointment and drops including Muro 128
- Systemic (nasal, inhaled, oral, parenteral, or topical) or ophthalmic corticosteroids **Note:** Inhaled corticosteroids are acceptable as long as the subject is on stable low doses and the dose is not expected to change for the duration of the study
- Cyclosporine ophthalmic emulsion
- Xiidra ® (lifitegrast ophthalmic solution)

Subjects requiring the use of prohibited medications must be discussed with the masked Medical Monitor.

6.3.3 **Pregnancy Testing and Contraception**

Women of child-bearing potential (WOCBP) are defined as a premenopausal female capable of becoming pregnant. Women who are not WOCBP are those who have not had a menstrual cycle for at least 2 years or who have had hysterectomy, bilateral tubal ligation, or bilateral oophorectomy. Sexually active female subjects who are WOCBP must use at least 1 highly-effective method of contraception or at least 2 less effective methods of contraception (including 1 barrier method), starting at least 1 month prior to Day 0, and male subjects who are sexually active with women of childbearing potential must agree to use a double-barrier method of contraception. Per *ICH M3(R2) Non-Clinical Safety Studies for the Conduct of Human Clinical Trials and Marketing Authorization for Pharmaceuticals*, highly-effective methods are defined as "those, alone or in combination, that result in a low failure rate (i.e., less than 1% per year) when used consistently and correctly." FDA-approved contraceptive methods and estimated failure rates are summarized in Table 2.

Method	Failure Rate
Highly-Effective*	
Sterilization surgery for women	Less than 1%
Sterilization implant for women	Less than 1%
Sterilization surgery for men	Less than 1%
IUD Copper	Less than 1%
IUD with Progestin	Less than 1%
Implantable Rod	Less than 1%
Less-Effective	
Shot/ Injection	6%
 Oral Contraceptives "The Pill" * 	9%
• Patch	9%
Vaginal Contraceptive Ring	12%
Diaphragm with Spermicide	12-24%
Cervical Cap with Spermicide	17-23%
Male Condom	18%
Female Condom	21%
Spermicide Alone	28%

Table 2: FDA-Approved N	lethods of Contraception and Es	stimated Failure Rates
The second secon		

*(including Combined, Extended/ Continuous Use Combined Pill, and the "Mini Pill", Progestin only) Adapted from FDA Birth Control Guide www.FDA.gov/birthcontrol

Trefoil Therapeutics, Inc.	Clinical Study Protocol TTHX-001
Confidential and Proprietary	Amendment 1.0: September 8, 2020

The contraceptive plan for each subject should be discussed with the Investigator and will be determined at the Investigator's discretion including the use of a double-barrier (e.g.; male condom, female diaphragm with spermicide) in male subjects.

6.4 Study Procedures

6.4.1 Informed Consent

A sample Informed Consent Form (ICF) will be provided by Trefoil and will be in accordance with 21 CFR 312 Part 50 Subpart B Section 50.25. The sample ICF will be revised by the investigational site to include site-specific information and required language, as needed. The Investigator ensure IRB/IEC review and approval of ICF.

Written informed consent will be obtained from all potential subjects prior to any study-specific assessments are conducted. Informed consent will be obtained in accordance with 21 CFR Part 50 Protection of Human Subjects.

Alternative therapies will be discussed with each potential participant including other pharmacologic therapies, investigational treatments (if available), or watchful waiting. Informed consent will include a HIPAA release/ waiver.

6.4.2 **Demographics**

Demographic information will be recorded, including:

- Age
- Sex
- Race
- Ethnicity

The subject's height and weight will be measured and recorded. Height should be measured without shoes and weight should be measured with minimal street clothing. If the Investigator feels that the subject is a reliable source, self-reported height and weight may be recorded.

6.4.3 Medical History and Ocular History

During the Screening/ Pretreatment Period, the Investigator (or designee) will review the medical history of all potential subjects to document all relevant clinically significant baseline medical conditions, concomitant medication use, and to determine study eligibility. Medical History Assessment will include review of all available medical records and patient interview. Assessment of all eligibility criteria should be evidenced in the study records. Medical history will include a detailed disease history regarding onset, severity, and history of prior therapy.

In addition to the data collected in demographics and medical history, specific information will be collected regarding each subject's ocular history, including:

- Present condition
 - Duration (date/ age of onset)
 - Single or both eyes involved
 - Associated symptoms
- Other corneal dystrophies
- Contact lens use and history
- Past ocular surgery (including LASIK)

- History of ocular trauma
- Family history of ocular conditions
- Allergies
- Diabetes
- Hypertension
- Autoimmune disease

Additional relevant medical history will also be recorded.

6.4.4 Comprehensive Ocular Examination

A comprehensive ocular examination will be performed at Screening and Day 56 and will include slit-lamp biomicroscopy and a dilated examination of the lens, fundus, and vitreous.

6.4.5 Specular Microscopy

Specular microscopic images will be obtained of the center of the cornea at every visit. The center of the cornea is defined as the region of the cornea above the pupil. If a subject is to be dilated at a visit, specular microscopy must be performed prior to dilation.

Endothelial cell density, percent hexagonality and the coefficient of variation will be assessed from specular microscope images. A centralized reading center with experienced readers

will be responsible for the choice and certification of equipment and training of technicians as well as reading images and conducting image analysis.

Common sources of variability in specular microscopy are:

- difficulty in returning to same location on the cornea at each visit
- poor image quality (less than 100 countable cells)
- technician error
- improper reader analysis
- maintaining equipment calibration/alignment

All individuals responsible for on-study image capture must be certified by the reading center.

To address differences in location of the image within a given area of the cornea, three acceptable images should be taken at each location, at each visit. The density from at least one preferred image should be determined.

Prior to obtaining baseline images (Day 0), the technician will obtain an initial set of images for an evaluation of image quality. Training (or retraining) will be performed as necessary and include the following important points:

A preferred image has:

- Distinct cells,
- At least 100 identifiable/ countable cells as a minimum (150 cells preferred), and
- Cells that can be grouped in a uniform area.

To capture a good image:

- Make sure the subject is comfortable,
- Instruct the subject to blink,
- Instruct subject not to move and to open eyes wide,

- Instruct subject to focus on the fixation light,
- If necessary, use the manual setting. Note: Use of the manual setting may require additional training

A calibration grid may be obtained from the specular microscope manufacturer.

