4.1 Efficacy Endpoints

4.1.1 **Primary Endpoint**

The primary endpoint is the change in average ECD in the center of the cornea of the study eye from baseline to Day 56; the center of the cornea is defined as the region over the pupil. Each treatment group will be compared to the vehicle group with no correction for multiple comparisons.

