4.10 Data to be Entered into the Database

Endothelial cell count/ density measured by the central reading facility is the primary efficacy endpoint for this study. The data generated by the central reading facility will be reconciled (Subject ID, date, time, timepoint) with the clinical database and the results will be uploaded into the database under a Quality and Data Transfer Specifications Agreement. Uploaded data will then be 100% quality checked (e.g.; sourced data verified) with the data at the central reading facility.

Other data and results generated by the investigational site will be data entered directly into the electronic data capture (EDC) system. All data in the EDC will be monitored and critical variables will be 100% source data verified.

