5.1 Inclusion Criteria

- 1. Male or female, 18 years of age or older
- 2. Able and willing to provide informed consent

Trefoil Therapeutics, Inc.	Clinical Study Protocol TTHX-001
Confidential and Proprietary	Amendment 1.0: September 8, 2020

- 3. Fuchs Endothelial Corneal Dystrophy, pseudophakic bullous keratopathy, or endothelial dysfunction/ insufficiency due to surgical intervention diagnosed more than 6 months prior to Study Day 0 in the study eye
- 4. Intact anterior chamber anatomy (if posterior capsule is open or absent, absence of vitreous in the anterior chamber must be verified or enrollment approved by the Medical Monitor) in the study eye and no structural abnormalities that would make intracameral injection difficult
- 5. Able to obtain clear corneal endothelial cell (CEC) morphology and central CEC counts by specular microscopy from both eyes as determined by the central reading facility
- 6. Central endothelial cell count of < 2000 mm² in at least one eye as determined by the central reading facility during the screening period

Note: FECD patients with dense central guttae may not be countable and therefore, not eligible

- 7. Best Corrected Visual Acuity (BCVA) of at least 15 letters (per Early Treatment of Diabetic Retinopathy Study [ETDRS] testing) (approximately 20/400), in each eye
- 8. If female, are non-pregnant, non-lactating Subjects who are women of childbearing potential (WOCBP) must be using an acceptable method of birth control [e.g., an Intrauterine Contraceptive Device (IUCD), hormonal contraceptives, or double barrier method] starting at least 1 month prior to Study Day 0 and for the duration of the study. If a female subject is currently abstinent, they must agree to use a double barrier method of birth control before they become sexually active. Men who are sexually active with a woman of childbearing potential must agree to use a double barrier method.

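### Three central specular images are taken at each visit, but the primary-endpoint ECD may rest on one; averaging every qualifying image would be a cheap gain in precision

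*Protocol*

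**What the plan says.** Section 4.1.1 defines the endpoint: "The primary endpoint is the change in average ECD in the center of the cornea of the study eye from baseline to Day 56". It does not say what the average is taken over. Section 4.10 names the source of the value: "Endothelial cell count/ density measured by the central reading facility is the primary efficacy endpoint for this study".

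Section 6.4.5 sets the measurement rule. Among common sources of variability it lists "difficulty in returning to same location on the cornea at each visit" first. Its response is replication: "To address differences in location of the image within a given area of the cornea, three acceptable images should be taken at each location", and this is to be done at every visit. The reading requirement that follows is "The density from at least one preferred image should be determined". A preferred image has distinct cells, at least 100 that can be counted (150 is the target), and cells that can be grouped in a uniform area.

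The note to inclusion criterion 6 in section 5.1 recognises that some corneas are hard to read: "FECD patients with dense central guttae may not be countable".

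Table 1 plans 17 vehicle, 20 low-dose, 17 mid-dose and 17 high-dose subjects, 71 in all. Section 4.1.1 compares each dose with vehicle.

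**The concern.** Taking three images helps the endpoint only if more than one is read and the results are combined. The reading rule asks for one. More may be read, but nothing requires it, and nothing makes the number read the same at baseline and Day 56. A reading center could follow the text exactly and still discard the replication that the preceding sentence was written to obtain.

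This is a measurement rule that the protocol states, and it acts before any analysis. A statistical analysis plan can say how several readings are combined, but it cannot average readings that were never made.

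What is at stake is precision. With 17 to 20 subjects per arm, the scatter of the ECD change limits what each comparison with vehicle can detect, and the images that could reduce it are already being collected. The rule applies to all arms alike and readers are masked, so no bias between arms is claimed.

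**Working it through.** **Plan's own figure.** The available text gives no power, SD, effect size or alpha (section 9 is blank in this copy), so there is nothing to reproduce. Table 1 adds up: rows 9 + 18 + 44 = 71; columns 17 + 20 + 17 + 17 = 71.

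**Inputs from the protocol.** Three images taken per visit; at least one read; arms of 17 (vehicle), 20, 17 and 17.

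**Assumptions.**
- s is the share of the variance of the ECD change that comes from independent image-to-image scatter when one image is read at each visit. The protocol does not give it; 0.1, 0.3, 0.5 and 0.7 are shown.
- Image scatter is equal at the two visits, so each contributes s/2.
- Any shift common to all images at a visit (calibration, reader, whole-visit displacement) lies outside s and is not reduced.
- Two-sample t test on change, two-sided 0.05, true effect 0.8 of the single-image SD.

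**Variance ratio against one image at both visits.**
- Three images at both visits: r = 1 − s + s/3 = 1 − (2/3)s.
- Three at one visit, one at the other: r = 1 − s/2 + s/6 = 1 − s/3.
- Two at both visits: r = 1 − s + s/2 = 1 − s/2.

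**Power.** This is noncentral t with noncentrality 0.8 / √(r(1/n₁ + 1/n₂)) and n₁ + n₂ − 2 degrees of freedom. With one image at both visits (r = 1), power is 0.619 at 17 vs 17 and 0.655 at 20 vs 17. The difference detectable with 80% power at 17 vs 17 is 0.991 SD, and it scales with √r.

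| s | r, three at both visits | Equivalent n per arm (17/r) | Detectable difference, 17 vs 17 (SD) | Power, 17 vs 17 | Power, 20 vs 17 |
|---|---|---|---|---|---|
| one image | 1 | 17 | 0.991 | 0.619 | 0.655 |
| 0.1 | 0.933 | 18.2 | 0.957 | 0.649 | 0.685 |
| 0.3 | 0.800 | 21.2 | 0.886 | 0.715 | 0.751 |
| 0.5 | 0.667 | 25.5 | 0.809 | 0.791 | 0.823 |
| 0.7 | 0.533 | 31.9 | 0.724 | 0.872 | 0.898 |

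**Partial replication, power at 17 vs 17.**

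| s | Three at one visit, one at the other | Two at both visits |
|---|---|---|
| 0.1 | 0.633 | 0.641 |
| 0.3 | 0.664 | 0.689 |
| 0.5 | 0.698 | 0.743 |
| 0.7 | 0.733 | 0.801 |

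Replicating at one visit only gives up about half or more of the gain in power. That is the reason for using the same rule at baseline and Day 56.

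**Workload, study eye, baseline and Day 56.** At the minimum, 71 × 2 = 142 readings. With three images each, 71 × 2 × 3 = 426, which is 284 more.

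**The case against.** The strongest reply is that the sentence is only a floor. It does not tell the reading center to use one image or to drop the others. The endpoint is already called an average, and three images are taken for a stated purpose, so averaging is a natural reading. How replicates become one visit value is often left to a reading-center manual or the statistical analysis plan, neither of which is at hand. The floor also has a use: in eyes with guttae or low density, perhaps only one image will meet the preferred standard.

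The size is open to challenge too. The variance share and the effect size are both assumed, and the gain at 17 vs 17 runs from 3 to 25 percentage points with nothing in the protocol to choose between them. If only two images qualify, the gain is smaller, as the second table shows. Images that overlap are not independent and would add less. A model other than a t test on change would give other figures.

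Much of this stands as a limit on size. The reading center may well read all three already, in which case the edit only records practice. It does not remove the point. The text fixes a minimum of one, the average is undefined, and an average of one image satisfies it. Difficult corneas justify a fallback when fewer than three images qualify; they do not justify a minimum of one for every eye.

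**Conclusion.** The point holds, as an inexpensive improvement that should be made. It does not show an error that invalidates the endpoint. Section 6.4.5 collects replication for a stated reason and then lets the primary endpoint be read without it, and with different numbers of images at the two visits that form the change.

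If one image would otherwise be read, and three independent images qualify at both visits, image-scatter variance falls by two thirds and total change-score variance by (2/3)s. Over s from 0.1 to 0.7, that is worth between about 1 and 15 extra subjects per arm at 17 per arm (17/r − 17). At s = 0.1 the benefit is small; at 0.5 or more it is material. Confidence is medium, because s is unknown and present reading practice may already be better than the text requires.

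**What to change.** Replace the sentence on the minimum number of images in section 6.4.5 with:

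> Density is determined for every image that meets the preferred-image criteria (target three) at each visit, and the visit ECD is their simple unweighted mean. If fewer than three qualify, the mean of those that do is used and the number is recorded. The same rule applies at baseline and Day 56.

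Require this at least for the study eye at those two visits. It also says what the average in section 4.1.1 is taken over, and an eye with a single qualifying image still contributes a value.

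The cost is reading time at the existing reading center: at most 284 additional study-eye readings over the two visits. No new images, visits or readers are needed. The downside is that, if image scatter proves a small part of the variance, the extra reading buys little.

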6.4.6 Best corrected Visual Acuity (BCVA)

Wherever possible best corrected visual acuity (BCVA), **should be measured between** 07:00 AM and 11AM, (with the exception of the Observational Sub-Study Visit 1 PM visit which is to be measured after noon). Site staff should follow their standard procedures for conducting BCVA using Early Treatment Diabetic Retinopathy Study (ETDRS) testing. BCVA at a single site should be done consistently throughout the study using the same equipment, lighting conditions etc.

BCVA testing should precede any examination requiring contact with the eye, including measurement of IOP, and should be performed prior to instillation of any of any dye or drops to dilate or anesthetize the eye. Refraction should be performed prior to measurement of BCVA and the appropriate correction worn in a trial frame during visual acuity testing.

6.4.7 Slit Lamp Biomicroscopy

The slit lamp biomicroscopy examination will be performed at every visit with the slit lamp using a beam of 1.0 mm height and 1.0 mm width with the beam at maximum luminance and using the high powered lens. The subject will be seated during the examination. This procedure should be conducted in the same manner for all subjects and will include an assessment of each of the following:

- Lens
- Corneal Edema
 - Assessed in the central region
- Corneal Opacity
- Conjunctiva Bulbar Injection
- Sclera Ciliary Flush
- Anterior Chamber Cells
- Anterior Chamber Flare
- Evaluation of the intra-ocular lens (IOL) and the posterior capsule (for subjects with pseudophakic IOL)

These assessments will be graded according to the criteria described in Table 3.

Grade	Corneal Edema (central)	Corneal Opacity	Conjunctiva Bulbar Injection	Sclera Ciliary Flush	Conjunctival Hyperemia (vasodilation)
0	Absent	Absent	Absent	Absent	Absent
1	Mild	Mild	Mild	Mild	Some
2	Moderate	Moderate	Moderate	Moderate	Moderate
3	Severe	Severe	Severe	Severe	Excessive
Grade	Anterior Cl	Anterior Chamber Cells		Anterior Chamber	Flare
0	No cells	No cells seen		None	
0.5+	1 - 5 c	1 - 5 cells		-	
1+	6 - 15 0	6 - 15 cells		Faint	
2+	16 - 25 cells		Modera	ate (iris and lens deta	il clear)
3+	26 - 50	26 - 50 cells		d (iris and lens detail	ls hazy)
4+	> 50 cells		Intens	e (fibrin or plastic aq	(ueous)

Table 3: Grading of Slit Lamp Biomicroscopy Assessments

